5.3.4.8 Treatment Planning and Dosimetry

5.3.4.8.1 Planning System Requirements

The requirements for planning systems are described in the separate Radiation Manual.

5.3.4.8.2 Beam Arrangements

There is no prescribed beam arrangement; individual departments are free to use established treatment protocols provided 3 or more fields are employed.

Inverse Planned IMRT, volumetric modulated arc therapy and techniques are allowed if sites are credentialed.

5.3.4.8.3 Lipiodol Injection for Target Volume Delineation and Image Guidance

The use of bladder tumour demarcation with lipiodol injection through flexible cystoscopy is permitted if used as standard of care at the treating center to optimize radiation planning and image guidance. Lipiodol may be injected in the bladder wall prior to radiation planning consistent with previous publications highlighting the benefits of injecting small 0.25ml deposits

circumferential pattern around the primary tumour or resection site, with excess lipiodol removed with irrigation [23]. This must be done prior to radiation planning and commencement.

5.3.4.8.4 Treatment Techniques not permitted

- Techniques utilising beam energies less than 6MV are not permitted.
- Techniques delivered using the following equipment is not permitted
 - Gamma Knife
 - Helical Tomotherapy
 - CyberKnife
 - Protons

5.3.4.8.5 Compensation and heterogeneity corrections

The requirements for compensation and heterogeneity corrections are in the Radiation Manual

5.3.4.8.6 Dose distribution/Reporting

The requirements for dose distribution/reporting are in the Radiation Manual

5.3.4.9 Treatment Verification and Delivery

For all fractions, treatment verification is based on soft tissue based placement derived from a pre-treatment cone beam CT. All isocentre offsets identified on CBCT should be corrected daily (i.e. 0cm action threshold – any offset greater than or equal to 1mm should be corrected).

If the bladder size is larger than the PTV size the patient will be requested to void their bladder and another verification CBCT should be performed prior to treatment delivery.

5.3.4.9.1 Treatment Verification

Treatment Verification comprises the following:

- Daily treatment unit based cone beam CT prior to treatment to ensure soft tissue based Isocentre placement (all fractions)
- Repeat treatment unit based cone beam CT prior to treatment where an initial target CT demonstrates a residual bladder volume that does not fit into a conventional 1.5cm plan.

Treatment verification using daily treatment unit based cone beam verification CT should be completed from commencement of treatment without interruption.

Where a treatment unit based cone beam CT cannot be completed, alternative management strategies will require:

- Use of standard departmental imaging protocols (2D planar KV or MV EPI bone based) on-line and with a zero threshold value.

The reasons for interruption to daily treatment unit based verification cone beam CT must be recorded.

5.3.4.9.2 Data Submission:

Details of data submission requirements are found in the PCR-MIB Radiation Manual.

5.3.4.9.3 Treatment Equipment Specifications/Physical factors

All participants must be treated using external beam radiotherapy on a linear accelerator.

The following specifications apply to equipment used:

- Energy: 6MV or greater
- MLC size: 1.0cm or smaller
- Cone Beam Factors include:
- Minimum 15cm scan length
- Volumetric with minimum slice spacing of 3mm
- kVp greater or equal to 120kVp

5.4 Concomitant Medications/Vaccinations (allowed & prohibited)

Medications or vaccinations specifically prohibited in the exclusion criteria are not allowed during the ongoing trial. If there is a clinical indication for one of these or other medications or vaccinations specifically prohibited during the trial, discontinuation from trial therapy or vaccination may be required. The investigator should discuss any questions regarding this with the Coordinating principal investigator. The final decision on any supportive therapy or vaccination rests with the investigator and/or the participant's primary physician.

5.4.1 Acceptable Concomitant Medications

During the period of chemoradiotherapy, dexamethasone 4 mg IV premedication given prior to cisplatin is permitted and allowed to continue at dose \leq 4mg orally daily for 2 days after administration is permissible. After completion of chemoradiotherapy corticosteroids equivalent up to 10mg per day of prednisone is permissible upon discussion with study chair.

All treatments that the investigator considers necessary for a participant's welfare may be administered at the discretion of the investigator in keeping with the community standards of medical care. All concomitant medication will be recorded on the case report form (CRF) including all prescription, over-the-counter (OTC), herbal supplements, and IV medications and fluids. If changes occur during the trial period, documentation of drug dosage, frequency, route, and date may also be included on the CRF.

All concomitant medications received within 28 days before the first dose of trial treatment and 30 days after the last dose of trial treatment should be recorded. Concomitant medications administered after 30 days after the last dose of trial treatment should be recorded for SAEs as defined in Section 7.2.

5.4.2 Prohibited Concomitant Medications

Participants are prohibited from receiving the following therapies during the Screening and Treatment Phase (including retreatment for post-complete response relapse) of this trial:

- Antineoplastic systemic chemotherapy or biological therapy
- Immunotherapy not specified in this protocol
- Chemotherapy not specified in this protocol
- Investigational agents other than pembrolizumab
- Live vaccines within 30 days prior to the first dose of trial treatment and while participating in the trial. Examples of live vaccines include, but are not limited to, the following: measles, mumps, rubella, varicella/zoster, yellow fever, rabies, BCG, and typhoid vaccine.
- Systemic glucocorticoids for any purpose other than to modulate symptoms from an event of clinical interest of suspected immunologic etiology. The use of physiologic doses of corticosteroids is allowed. The use of dexamethasone with cisplatin chemotherapy is permitted as described in 5.3.1.3.1

Participants who, in the assessment by the investigator, require the use of any of the aforementioned treatments for clinical management should be removed from the trial. Participants may receive other medications that the investigator deems to be medically necessary.

The Exclusion Criteria describes other medications which are prohibited in this trial.

There are no prohibited therapies during the Post-Treatment Follow-up Phase.

5.5 Rescue Medications & Supportive Care for Pembrolizumab

5.5.1 Supportive Care Guidelines

Participants should receive appropriate supportive care measures as deemed necessary by the treating investigator. Suggested supportive care measures for the management of adverse events with potential immunologic etiology are outlined below. The use of oral or intravenous treatment with corticosteroids as well as additional anti-inflammatory agents if symptoms do not improve with administration of corticosteroids is permitted if necessary. Note that several courses of steroid tapering may be necessary as symptoms may worsen when the steroid dose is decreased. For each disorder, attempts should be made to rule out other causes such as metastatic disease or bacterial or viral infection, which might require additional supportive care. The treatment guidelines below are intended to be applied when the investigator determines the events to be related to pembrolizumab.

Refer to Section 5.3.2.2 for timing for restarting treatment and discontinuation criteria.

It may be necessary to perform conditional procedures such as bronchoscopy, endoscopy, or skin photography as part of evaluation of the event.

- **Pneumonitis:**
 - For **Grade 2 events**, treat with systemic corticosteroids 1-2mg/kg prednisone or equivalent. When symptoms improve to Grade 1 or less, steroid taper should be started and continued over no less than 4 -6 weeks.

- For **Grade 3-4 events, or recurrent Grade 2**, immediately treat with systemic intravenous corticosteroids 1-2mg/kg prednisone or equivalent. When symptoms improve to Grade 1 or less, steroid taper should be started and continued over no less than 4 -6 weeks. Administer additional anti-inflammatory measures, as needed.
- Add prophylactic antibiotics for opportunistic infections in the case of prolonged steroid administration.
- Cisplatin and radiation can continue despite pneumonitis if judged safe by investigators
- **Diarrhea/Colitis:**
 Participants should be carefully monitored for signs and symptoms of enterocolitis (such as diarrhea, abdominal pain, blood or mucus in stool, with or without fever) and of bowel perforation (such as peritoneal signs and ileus).
 - All participants who experience diarrhea/colitis should be advised to drink liberal quantities of clear fluids. If sufficient oral fluid intake is not feasible, fluid and electrolytes should be substituted via IV infusion. For Grade 2 or higher diarrhea, consider GI consultation and endoscopy to confirm or rule out colitis.
 - For **Grade 2 diarrhea/colitis** that persists greater than 3 days, treat with systemic corticosteroids 1-2mg/kg prednisone or equivalent., then tapering over 4-6 weeks. If Grade 2 diarrhea persists despite steroids for more than 3 days, management should be escalated to treat patient with IV steroids, and pembrolizumab withheld until colitis resolves to Grade 0-1
 - For **Grade 3 or 4 diarrhea/colitis**, treat with systemic intravenous corticosteroids 1-2mg/kg prednisone or equivalent.
 - When symptoms improve to Grade 1 or less, steroid taper should be started and continued over no less than 4 weeks.
- **Type 1 diabetes mellitus (if new onset, including diabetic ketoacidosis [DKA]) or ≥ Grade 3 Hyperglycemia, if associated with ketosis (ketonuria) or metabolic acidosis (DKA)**
 - For **T1DM or Grade 3-4 Hyperglycemia**
 - Insulin replacement therapy is recommended for Type I diabetes mellitus and for Grade 3-4 hyperglycemia associated with metabolic acidosis or ketonuria.
 - Evaluate patients with serum glucose and a metabolic panel, urine ketones, glycosylated hemoglobin, and C-peptide.
- **Hypophysitis:**
 - For **Grade 2** events, treat with corticosteroids. When symptoms improve to Grade 1 or less, steroid taper should be started and continued over no less than 4 weeks. Replacement of appropriate hormones may be required.

- For **Grade 3-4** events, treat with an initial dose of IV corticosteroids followed by oral corticosteroids. When symptoms improve to Grade 1 or less, steroid taper should be started and continued over no less than 4 weeks. Replacement of appropriate hormones may be required as the steroid dose is tapered.
- **Hyperthyroidism or Hypothyroidism:**
Thyroid disorders can occur at any time during treatment. Monitor patients for changes in thyroid function (at the start of treatment, periodically during treatment, and as indicated based on clinical evaluation) and for clinical signs and symptoms of thyroid disorders.
 - **Grade 2** hyperthyroidism events (and **Grade 2-4** hypothyroidism):
 - In hyperthyroidism, non-selective beta-blockers (e.g. propranolol) are suggested as initial therapy.
 - In hypothyroidism, thyroid hormone replacement therapy, with levothyroxine or liothyroinine, is indicated per standard of care.
 - **Grade 3-4** hyperthyroidism
 - Treat with non-selective beta-blockers (eg, propranolol) or thionamides as appropriate. Replacement of appropriate hormones may be required as the steroid dose is tapered.
- **Hepatic:**
 - For **Grade 2** events, monitor liver function tests more frequently until returned to baseline values (consider weekly).and treat with 0.5-1mg systemic prednisone or equivalent.
 - For **Grade 3-4** events, treat with intravenous 1-2mg/kg corticosteroids for 24 to 48 hours then 0.5-1mg systemic prednisone or equivalent.
 - When symptoms improve to Grade 1 or less, a steroid taper should be started and continued over no less than 4 weeks.
- **Nephritis:**
 - For **Grade 2** events, treat with corticosteroids.
 - For **Grade 3-4** events, treat with systemic corticosteroids. Permanently discontinue pembrolizumab.
 - When symptoms improve to Grade 1 or less, steroid taper should be started and continued over no less than 4 weeks.

Management of Infusion Reactions: Signs and symptoms usually develop during or shortly after drug infusion and generally resolve completely within 24 hours of completion of infusion.

Table 7 shows treatment guidelines for participants who experience an infusion reaction associated with administration of pembrolizumab.

Table 7: Infusion Reaction Treatment Guidelines

NCI CTCAE Grade	Treatment	Premedication at subsequent dosing
Grade 1 Mild reaction; infusion interruption not indicated; intervention not indicated	Increase monitoring of vital signs as medically indicated until the participant is deemed medically stable in the opinion of the investigator.	None
Grade 2 Requires infusion interruption but responds promptly to symptomatic treatment (e.g., antihistamines, NSAIDS, narcotics, IV fluids); prophylactic medications indicated for <=24 hrs.	
Stop Infusion and monitor symptoms. Additional appropriate medical therapy may include but is not limited to:
 
 IV fluids Antihistamines NSAIDS Acetaminophen Narcotics 
Increase monitoring of vital signs as medically indicated until the participant is deemed medically stable in the opinion of the investigator.
 
If symptoms resolve within one hour of stopping drug infusion, the infusion may be restarted at 50% of the original infusion rate (e.g., from 100 mL/hr to 50 mL/hr). Otherwise dosing will be held until symptoms resolve and the participant should be premedicated for the next scheduled dose.
 
Participants who develop Grade 2 toxicity despite adequate premedication should be permanently discontinued from further trial treatment administration.
	Participant may be premedicated 1.5h (\pm 30 minutes) prior to infusion of pembrolizumab (MK-3475) with: Diphenhydramine 50 mg po (or equivalent dose of antihistamine). Acetaminophen 500-1000 mg po (or equivalent dose of antipyretic).
Grades 3 or 4 Grade 3: Prolonged (i.e., not rapidly responsive to symptomatic medication and/or brief interruption of infusion); recurrence of symptoms following initial improvement; hospitalization indicated for other clinical sequelae (e.g., renal impairment, pulmonary infiltrates) Grade 4: Life-threatening; pressor or ventilatory support indicated	
Stop Infusion. Additional appropriate medical therapy may include but is not limited to:
 
 IV fluids Antihistamines NSAIDS Acetaminophen Narcotics Oxygen Pressors Corticosteroids Epinephrine 
Increase monitoring of vital signs as medically indicated until the participant is deemed medically stable in the opinion of the investigator.
 
Hospitalization may be indicated.
 
Participant is permanently discontinued from further trial treatment administration.
	No subsequent dosing

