5.3.2.2 Pembrolizumab

Adverse events (both non-serious and serious) associated with pembrolizumab exposure may represent an immunologic etiology. These adverse events may occur shortly after the first dose or several months after the last dose of treatment. Pembrolizumab must be withheld for drug-related toxicities and severe or life-threatening AEs as per Table 6 below. See Section 5.5.1 for supportive care guidelines, including use of corticosteroids.

Table 6: Dose Modification Guidelines for Pembrolizumab Drug-Related Adverse Events

General instructions:				
Immune-related AEs	Toxicity grade or conditions (CTCAEv4.0)	Action taken to pembrolizumab	irAE management with corticosteroid and/or other therapies	Monitor and follow-up
Pneumonitis	Grade 2	Withhold	
 Administer corticosteroids (initial dose of 1-2 mg/kg prednisone or equivalent) followed by taper 	
 Monitor participants for signs and symptoms of pneumonitis Evaluate participants with suspected pneumonitis with radiographic imaging and initiate corticosteroid treatment Add prophylactic antibiotics for opportunistic infections
	Grade 3 or 4, or recurrent Grade 2	Permanently discontinue		
Diarrhea / Colitis	Grade 2 or 3	Withhold	
 Administer corticosteroids (initial dose of 1-2 mg/kg prednisone or equivalent) followed by taper 	
 Monitor participants for signs and symptoms of enterocolitis (ie, diarrhea, abdominal pain, blood or mucus in stool with or without fever) and of bowel perforation (ie, peritoneal signs and ileus). Participants with \geq Grade 2 diarrhea suspecting colitis should consider GI consultation and performing endoscopy to rule
	Grade 4	Permanently discontinue		

				
 out colitis. Participants with diarrhea/colitis should be advised to drink liberal quantities of clear fluids. If sufficient oral fluid intake is not feasible, fluid and electrolytes should be substituted via IV infusion.
AST / ALT elevation or Increased bilirubin	Grade 2	Withhold	
 Administer corticosteroids (initial dose of 0.5- 1 mg/kg prednisone or equivalent) followed by taper 	
 Monitor with liver function tests (consider weekly or more frequently until liver enzyme value returned to baseline or is stable

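### For Grade 2 pembrolizumab-related diarrhoea/colitis, Section 5.5.1 brings in withholding more than 6 days later than Table 6, which governs

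*Combined protocol and SAP*

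**What the plan says.** **Section 5.3.2.2 and Table 6.** The lead-in reads: "Pembrolizumab must be withheld for drug-related toxicities and severe or life-threatening AEs as per Table 6 below". In the diarrhoea/colitis row, Grades 2 and 3 share one action, which is to withhold, and Grade 4 means permanent discontinuation. No duration or persistence condition is attached. The steroid column reads "Administer corticosteroids (initial dose of 1-2 mg/kg prednisone or equivalent) followed by taper". The same section adds: "See Section 5.5.1 for supportive care guidelines, including use of corticosteroids".

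**Section 5.5.1, Grade 2 diarrhoea/colitis.** The bullet concerns an event "that persists greater than 3 days, treat with systemic corticosteroids 1-2mg/kg prednisone or equivalent", "then tapering over 4-6 weeks". It continues: "If Grade 2 diarrhea persists despite steroids for more than 3 days, management should be escalated" to IV steroids, with "pembrolizumab withheld until colitis resolves to Grade 0-1". This is its only mention of withholding. The opening of Section 5.5.1 describes its measures as suggestions, applies them to events the investigator has judged related to pembrolizumab, and sends the reader to Section 5.3.2.2 for restart timing.

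**Section 5.3.3.** After a delay for a Table 6 event, pembrolizumab may resume once toxicity is Grade 1 or lower and prednisolone (or equivalent) is at 10 mg or below.

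**The concern.** Both texts are written for the clinician managing the event, and they give different answers to whether the next dose should be held. Under Table 6, a patient with Grade 2 diarrhoea/colitis attributed to pembrolizumab is held at once. Under the 5.5.1 bullet, the same patient passes through an untreated interval and then a course of steroids before withholding is mentioned.

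Section 5.5.1 is where a clinician looks for colitis management, and Section 5.3.2.2 sends the reader there. Someone working from the bullet alone could give pembrolizumab while immune-related colitis is active, or during the first days of 1-2 mg/kg steroids. Sites could also treat the same event differently.

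**Working it through.** The main check is a comparison of texts; the arithmetic is short. The plan states no figure of its own on this point.

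**1. Same event, grade and attribution.** Table 6 covers drug-related Grade 2 or 3 diarrhoea/colitis. Section 5.5.1 applies when the investigator considers the event related to pembrolizumab. A Grade 2 case therefore falls under both.

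**2. Action over time.**

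| Days since Grade 2 began | Table 6 | Section 5.5.1 bullet |
|---|---|---|
| Up to 3 | Withhold | No steroids, no mention of withholding |
| More than 3, then up to 3 days on steroids | Withhold | Steroids 1-2 mg/kg, no mention of withholding |
| After more than 3 days on steroids | Withhold | IV steroids and withhold |

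Gap in the withholding trigger: (more than 3) + (more than 3) = more than 6 days, against no stated wait in Table 6.

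**3. What the gap could mean for one dose (illustration only).** Pembrolizumab is given every 21 days. Assume that onset is equally likely on any day of a cycle, that further doses remain, and that dosing is exactly on schedule. For an event staying at Grade 2 for d days, the chance that a dose falls due while Table 6 says hold and the bullet does not is about min(d, 6)/21:

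- d = 3: 3/21 = 14%
- d = 6 or more: 6/21 = 29%, using 6 days as the minimum gap

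These are chances per event. The documents give no Grade 2 colitis rate, so they cannot be turned into a number of patients.

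**4. Which text governs.** The lead-in to Table 6 is mandatory. Section 5.3.1.4.3 makes continued dosing conditional on the absence of Table 6 toxicities that require withholding or discontinuation. Section 5.5.1 calls its own content suggested. Section 5.3.2.2 refers to Section 5.5.1 for supportive care, including steroids, but ties withholding to Table 6. All of this supports Table 6 on withholding.

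**5. The bullet against the rest of Section 5.5.1.** Among the immune-event bullets, Grade 2 diarrhoea/colitis alone has its own withholding trigger and a waiting period. Grade 2 pneumonitis starts steroids without a wait. The only other statement there on stopping pembrolizumab, for Grade 3-4 nephritis, agrees with Table 6. This suggests a drafting slip rather than an intended exception.

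**The case against.** The strongest reply is that the plan already has a controlling rule. Table 6 is mandatory and Section 5.5.1 is advisory. Adverse events are also reviewed close to each scheduled dose, and flow-chart footnote c (Section 6.1) makes dosing depend on that review. Harm would require a site to follow a suggestion over a requirement. This stands, and it is why the correction is minor. It does not make the bullet right: the review identifies the event, but the two texts still disagree on whether Grade 2 is a reason to hold.

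A second reply is that the wait allows time to establish the cause. Section 5.5.1 already confines its guidance to events judged related to pembrolizumab, so that step has been taken.

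A reader might also infer three stronger points, which the documents do not support.

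- *That the steroid start times contradict each other.* Table 6 gives one steroid action for Grades 2 and 3 together and states no start time, and Section 5.3.2.2 refers to Section 5.5.1 for steroid use. The 3-day condition can be read as the grade-specific detail.
- *That the bullet and Section 5.3.3 set conflicting ends to the hold.* The grade threshold is the same. The bullet omits the 10 mg limit, but Section 5.3.3 applies that limit by its own terms to any Table 6 delay. The limit matters: at assumed weights of 50 to 100 kg, 1-2 mg/kg is 50 to 200 mg. Even so, this is an omission that a cross-reference cures. A count of doses falling due above 10 mg would need the shape of the taper, which is not given. The general-instructions row of Table 6 is also blank in the text as read from the PDF, so restart wording there cannot be excluded.
- *That the unacceptable-toxicity endpoint is affected.* A single pembrolizumab delay of more than 6 weeks counts towards it (Section 3.1), but linking the bullet to that would need an event rate and a taper schedule. The documents give neither.

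**Conclusion.** The conflict on withholding is real and can be read directly from the two texts: no waiting period in Table 6, more than 6 days in the 5.5.1 bullet. Table 6 controls, so the bullet should be changed. The restart pointer in Section 5.5.1 is also incomplete, because the 10 mg prednisolone condition sits in Section 5.3.3, which it does not name.

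The textual conflict needs no assumption beyond the event being Grade 2 and attributed to pembrolizumab. The 14% to 29% illustration rests on the uniform-onset assumption and describes one event, not the trial. This is a minor patient-safety wording correction. Nothing here shows a defect in the endpoint, the sample size or the analysis.

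**What to change.** Reword the Grade 2 diarrhoea/colitis bullet in Section 5.5.1 along these lines:

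> Withhold pembrolizumab from onset of Grade 2, as Table 6 requires. If Grade 2 lasts beyond 3 days, start systemic corticosteroids at 1-2 mg/kg (prednisone or equivalent), with a 4 to 6 week taper. If it continues after more than 3 days of steroids, escalate to the IV route. Restart pembrolizumab only as Section 5.3.3 allows: Grade 1 or lower, and prednisolone (or equivalent) no higher than 10 mg.

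This keeps the existing steroid timing and changes only the point at which pembrolizumab is held. Also add Section 5.3.3 to the restart pointer at the head of Section 5.5.1.

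The cost is one bullet and one cross-reference, with ethics committee approval before implementation (Section 12.2). Sample size, data collection and analysis are unchanged. The differing resumption limits of 3 weeks (Section 5.3.1.4.4) and 12 weeks (Section 5.3.3) are a separate matter, which this change does not settle.

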	Grade 3 or 4	Permanently discontinue	
 Administer corticosteroids (initial dose of 1-2 mg/kg prednisone or equivalent) followed by taper 	
Type 1 diabetes mellitus (T1DM) or Hyperglycemia	Newly onset T1DM or Grade 3 or 4 hyperglycemia associated with evidence of β -cell failure	Withhold	
 Initiate insulin replacement therapy for participants with T1DM Administer anti-hyperglycemic in participants with hyperglycemia 	
 Monitor participants for hyperglycemia or other signs and symptoms of diabetes.
Hypophysitis	Grade 2	Withhold	
 Administer corticosteroids and initiate hormonal replacements as clinically indicated. 	
 Monitor for signs and symptoms of hypophysitis (including hypopituitarism and adrenal insufficiency)
	Grade 3 or 4	Withhold or permanently discontinue ¹		
Hyperthyroidism	Grade 2	Continue	
 Treat with non-selective beta-blockers (eg, propranolol) or thionamides as appropriate 	
 Monitor for signs and symptoms of thyroid disorders.
	Grade 3 or 4	Withhold or permanently discontinue ¹		
Hypothyroidism	Grade 2-4	Continue	
 Initiate thyroid replacement hormones (eg, levothyroxine or liothyroinine) per standard of care 	
 Monitor for signs and symptoms of thyroid disorders.
Nephritis	Grade 2	Withhold	
 Administer corticosteroids (prednisone 1-2 mg/kg or equivalent) followed by taper. 	
 Monitor changes of renal function
	Grade 3 or 4	Permanently discontinue		
Myocarditis	Grade 1 or 2	Withhold	
 Administer corticosteroids (initial dose of 1-2 mg/kg prednisone or equivalent) followed by taper 	
 Ensure adequate evaluation to confirm etiology and/or exclude other causes
	Grade 3 or 4	Permanently discontinue		
All other immune-related	Intolerable/ persistent Grade 2	Withhold	
 Based on type and severity of AE administer corticosteroids 	
 Ensure adequate evaluation to

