5.3.3 Timing of Dose Administration

Pembrolizumab should be administered on Day 1 of commencement of chemoradiotherapy after all procedures/assessments have been completed as detailed on the Trial Flow Chart (Section 6.0).

Pembrolizumab 200mg IV will be given in weeks 1, 4, 7, 10, 13, 16 and 19. Treatment may be administered up to 3 days before or after the scheduled day of each cycle due to administrative reasons.

In the event of a treatment delay due to an adverse event outlined in Table 6, patients may resume pembrolizumab within 12 weeks of the due dose so long as the toxicity has resolved to Grade 1 or less and the patient is on a dose of 10mg or less of prednisolone or equivalent. Subsequent dosing of pembrolizumab will continue until week 19, but not beyond this regardless of the total number of doses that the patient has received.

All trial treatments should be administered on an outpatient basis unless discussed with the Principal Investigator/Sponsor.

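### Section 5.5.1 prints two hepatic steroid doses without the per-kilogram unit: the Grade 2 dose contradicts Table 6, and the Grade 3-4 step-down appears to have the same slip

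*Combined protocol and SAP*

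**What the plan says.** Steroid dosing for hepatic immune events appears in two places.

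- **Table 6 (section 5.3.2.2), raised AST/ALT or bilirubin.** Grade 2: "Administer corticosteroids (initial dose of 0.5- 1 mg/kg prednisone or equivalent) followed by taper", with pembrolizumab withheld. Grade 3 or 4: "Administer corticosteroids (initial dose of 1-2 mg/kg prednisone or equivalent) followed by taper", with pembrolizumab permanently discontinued. No step-down dose is given.
- **Section 5.5.1, Hepatic.** Grade 2: more frequent liver function tests, and "treat with 0.5-1mg systemic prednisone or equivalent". Grade 3-4: "treat with intravenous 1-2mg/kg corticosteroids for 24 to 48 hours then 0.5-1mg systemic prednisone or equivalent". Once symptoms reach Grade 1 or less, "a steroid taper should be started and continued over no less than 4 weeks".

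Section 5.3.2.2 directs the reader onward: "See Section 5.5.1 for supportive care guidelines, including use of corticosteroids". Section 5.5.1 refers back to 5.3.2.2 only for restart timing and discontinuation, not for dose. Neither section says which prevails if they differ.

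**The concern.** For Grade 2 hepatic events the two sections give the same digits, drug, event and grade, but different units: milligrams in one, milligrams per kilogram in the other. They cannot both be right. The Grade 3-4 bullet prints the same unitised form for its step-down, in a sentence that begins with a per-kilogram dose.

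What is at stake is patient safety. On a literal reading of 5.5.1, Grade 2 immune hepatitis is left essentially untreated as far as steroids go, and in Grade 3-4 the steroid is almost stopped after 24 to 48 hours.

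The link to the primary endpoint is narrow. An under-treated Grade 2 event could worsen to Grade 3, or could hold up a pembrolizumab dose for more than 6 weeks; either counts as an unacceptable toxicity under section 3.1. The documents do not allow the size or direction of any such effect to be worked out. Grade 3-4 hepatic events already count as unacceptable toxicities and end pembrolizumab, whatever steroid dose follows.

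**Working it through.** The plan has no figure of its own to reproduce here. The check is a comparison of the dosing text, with simple arithmetic for the size of the gap.

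**1. Side by side**

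| Hepatic event | Table 6 | Section 5.5.1 | Reading |
|---|---|---|---|
| Grade 2, starting dose | 0.5-1 mg/kg | 0.5-1 mg | Contradiction |
| Grade 3-4, starting dose | 1-2 mg/kg | 1-2 mg/kg, intravenous | Agree |
| Grade 3-4, step-down | none given | 0.5-1 mg | No conflict; apparent unit omission |

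**2. Is a flat dose in keeping with the rest of 5.5.1?** The section gives seven numeric corticosteroid doses for immune events:

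- pneumonitis: 2, both mg/kg (the Grade 2 bullet reads "treat with systemic corticosteroids 1-2mg/kg prednisone or equivalent");
- diarrhoea/colitis: 2, both mg/kg;
- hepatic intravenous dose: 1, mg/kg;
- hepatic Grade 2 dose and Grade 3-4 step-down: 2, without /kg.

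So 2 + 2 + 1 = 5 of 7 are per kilogram, and the only exceptions are these two.

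**3. Size of the Grade 2 gap.** The documents give no body weight W, so 50-100 kg is assumed. Table 6 dose = W × 0.5 to W × 1 mg; ratio to the printed dose = (0.5 × W)/0.5 = (1 × W)/1 = W.

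| W (assumed) | Table 6 | Section 5.5.1 | Ratio |
|---|---|---|---|
| 50 kg | 25-50 mg | 0.5-1 mg | 50 |
| 70 kg | 35-70 mg | 0.5-1 mg | 70 |
| 100 kg | 50-100 mg | 0.5-1 mg | 100 |

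**4. Against the resumption ceiling.** After a delay for toxicity, section 5.3.3 lets pembrolizumab restart when the toxicity is down to Grade 1 or less and "the patient is on a dose of 10mg or less of prednisolone or equivalent". The printed hepatic dose is 0.5/10 to 1/10 = 5-10% of that ceiling. The Table 6 dose is 25/10 to 100/10 = 2.5 to 10 times it. A treatment dose far below the level regarded as low enough to restart the drug is not credible, and it leaves little to taper over four weeks.

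**5. Grade 3-4 step-down.** Reading the intravenous dose as prednisone equivalent, as Table 6 does, and comparing like ends of the ranges:

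- as printed: (1 × W)/0.5 = (2 × W)/1 = 2W, a single-step cut of 100-fold at 50 kg, 140-fold at 70 kg and 200-fold at 100 kg;
- with /kg restored: 1/0.5 = 2/1 = 2-fold.

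**6. Could the PDF reading have lost the unit?** Unlikely. The per-kilogram unit is intact earlier in the same Grade 3-4 sentence and in all four pneumonitis and colitis doses, while the form without it appears in two adjacent bullets.

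**The case against.** The strongest case on the other side is about weight, not fact.

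- **Section 5.5.1 is advisory and incomplete.** It presents its measures as suggestions, at the investigator's judgement, and gives no dose at all for nephritis, which is found only in Table 6. Investigators therefore need Table 6 anyway, and it has the right Grade 2 dose. This lowers the risk but does not remove the conflict: 5.3.2.2 sends readers to 5.5.1 specifically for corticosteroid use, and no order of precedence is stated.
- **A patient would not go without care.** Table 6 withholds pembrolizumab at Grade 2, liver tests are repeated more often, and further anti-inflammatory agents are allowed. That is fair. What a literal reading removes is an effective steroid dose, not all management.
- **A clinician would notice.** Probably so, since the slip is conspicuous. A multi-site protocol for an experimental combination should not depend on it.
- **The step-down is an inference.** No other text gives a Grade 3-4 step-down, so this half cannot be called a contradiction. The inference is strong, because the same sentence doses per kilogram and 0.5-1 is Table 6's per-kilogram range for Grade 2, but clinical confirmation is needed.
- **Laboratory abnormalities become adverse events only if the investigator judges them clinically significant** (sections 7.2.1 and 7.2.6), so a Grade 3-4 hepatic value is not strictly automatic as an unacceptable toxicity. One that needed intravenous steroids would almost certainly qualify.

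**Conclusion.** The concern holds. The Grade 2 hepatic dose in section 5.5.1 contradicts Table 6 by a factor equal to body weight in kilograms, which is 50 to 100 over the assumed 50-100 kg. The Grade 3-4 step-down is an apparent omission of the same unit. Its 100- to 200-fold cut rests on that weight range and on reading the intravenous dose as prednisone equivalent.

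This is a wrong dosing instruction in operative safety text and should be corrected. It has no bearing on the sample size, the stopping thresholds or the planned analyses, and no effect on the unacceptable-toxicity rate can be quantified from the documents.

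**What to change.** In the Hepatic part of section 5.5.1:

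- **Grade 2 bullet:** give the prednisone (or equivalent) dose as 0.5-1 mg/kg, matching Table 6.
- **Grade 3-4 bullet:** give the dose after the intravenous phase as 0.5-1 mg/kg, once the clinical team has confirmed that step-down, since Table 6 offers none to check against.

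Send sites a note of the correction. The cost is a two-bullet wording amendment and that note; nothing in the design or analysis changes.
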